1.1 Study design

This was a national, multi-center, open-label, phase IIIb trial to determine the efficacy and safety of treatment with ribociclib (LEE011) plus letrozole in patients with HR+, HER2-negative advanced (recurrent or metastatic) breast cancer.

In this trial a total of 500 patients from 100 centers were planned to be recruited.

The study was designed as an open-label, single-arm trial, hence no randomization took place.

The primary efficacy and safety analysis was conducted on all patient data at the time all patients who are still receiving study drug will have completed at least 24 weeks of treatment (or discontinued prematurely). The additional data for any patients continuing to receive study drug past these times, as allowed by the protocol, was further summarized in a report once these patients completed the study.

Three interim analyses were planned during the study. The first interim analysis was conducted one year after the first patient has been enrolled and included a preliminary analysis on safety. The second interim analysis was conducted 12 months after LPFV in the 30% pretreated and premenopausal cohort (=Cohort B, see section 2.2.1 Subgroup of interest) and included a preliminary analysis on safety, efficacy and quality of life. The third interim analysis took place 6 months after the last patient had been recruited into cohort A (see section 2.2.1 Subgroup of interest) and included a preliminary analysis on safety and efficacy.

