2.13 Other Exploratory analyses

Multivariate regression analysis to identify prognostic factors for Neutropenia respectively AST/ALT increase.

This analysis was not foreseen in the study protocol but included on request of the principal investigator for the presentation of interim and final results.

Two separate multivariate regression analyses were calculated for these interesting events (dependent variables):

1. Neutropenia, selected from AE data set via PTs “neutropenia” and/or “neutrophil count decreased”
2. Increase in ALT or AST: Selected from AE dataset via PTs “ALANINE AMINOTRANSFERASE INCREASED” and/or “ASPARTATE AMINOTRANSFERASE INCREASED”

The following effects (without interactions) were investigated by Type 3 estimates and Wald's confidence intervals for Odds ratios:

- Age at baseline (categorical): <60 years, 60-70 years, and >= 70 years
- BMI at baseline (categorical, rounded to integers): < 20, 20-25, 26-29, and >30 kg/m²
- Presence (no vs. yes) of bone metastases at study start
- Use of chemo therapy as prior antineoplastic medication (no vs. yes)
- Therapy line: 1st, 2nd, and >= 3rd

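### SAP 2.13 gives a rounded BMI of 30 no category and age 70 two; coded as written, patients with BMI 30 drop out of both exploratory prognostic-factor models

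*SAP*

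**What the plan says.** SAP section 2.13 describes two regression models that the protocol did not foresee. They were added at the principal investigator's request for presenting interim and final results. One looks for prognostic factors for neutropenia, the other for an increase in ALT or AST, and both use the same covariates. On method the SAP says: "The following effects (without interactions) were investigated by Type 3 estimates and Wald's confidence intervals for Odds ratios".

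Two of the covariates are continuous measurements cut into classes:

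- The classes for body mass index are given as "BMI at baseline (categorical, rounded to integers): < 20, 20-25, 26-29, and >30 kg/m²".
- The classes for patient age are given as "Age at baseline (categorical): <60 years, 60-70 years, and >= 70 years".

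Section 2.13 has no rule for a patient whose value fits no class or fits two. The imputation rules in SAP section 5.4 concern dates, non-target lesion response and censoring reasons; none of them covers a covariate without a class.

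**The concern.** Classes for a categorical covariate must cover every possible value once. Here the BMI classes have a hole and the age classes overlap.

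Rounding makes the hole larger. On unrounded BMI, a class starting above 30 would miss only a patient at exactly 30. After rounding to integers, the hole is a full unit wide and sits at the lower edge of the highest class. In a standard categorical regression, a record with an undefined class is treated as having a missing covariate, and the whole record leaves the model. The patient's outcome and other covariates (age, bone metastases, prior chemotherapy, therapy line) then go with it.

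The overlap is a different fault. A 70-year-old has a class, but the SAP does not say which, so two programmers could get different odds ratios for the two upper age classes from the same data.

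The models are exploratory, but their outcomes are not trivial. Protocol section 1.2.6 lists neutropenia and hepatobiliary toxicity among the important identified risks of ribociclib, and SAP section 2.8.1.1 makes both events of special interest.

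**Working it through.** **Step 1: coverage, from the SAP alone.** Each integer BMI from 15 to 45 and each integer age from 18 to 95 was checked against the stated classes.

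- BMI: 29 falls in 26-29, 31 falls in >30, and 30 falls in none. It is the only uncovered integer.
- Age: 69 falls in 60-70 only, 71 in >= 70 only, and 70 in both. It is the only integer covered twice.

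Both findings need no outside input.

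**Step 2: is there a figure to reproduce?** No. The documents give no BMI mean, SD or distribution for this trial, no number of patients in these models and no expected loss. Any size therefore rests on assumptions.

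**Step 3: share with a rounded BMI of 30.** With assumed mean m and SD s:

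- Normal: share = Φ((30.5 − m)/s) − Φ((29.5 − m)/s).
- Lognormal with the same mean and SD: σ = √ln(1 + (s/m)²), μ = ln m − σ²/2, share = Φ((ln 30.5 − μ)/σ) − Φ((ln 29.5 − μ)/σ).

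Worked example for the normal with m = 27, s = 5: Φ(0.70) − Φ(0.50) = 0.7580 − 0.6915 = 0.0666 (from unrounded values), or 6.7%.

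To turn shares into counts I use the planned total in SAP section 1.1: "In this trial a total of 500 patients from 100 centers were planned to be recruited".

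| Assumed mean, SD (kg/m²) | Normal | Lognormal | Patients of 500 |
|---|---|---|---|
| 24, 4 | 3.25% | 2.90% | 14-16 |
| 26, 5 | 5.79% | 4.88% | 24-29 |
| 27, 5 | 6.66% | 5.80% | 29-33 |
| 29, 4 | 9.64% | 9.20% | 46-48 |

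Over the whole grid (means 24 to 29, SDs 4 to 6, both distributions) the share runs from 2.9% to 9.6%.

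**Step 4: where the loss falls.** It is confined to the lower edge of the highest BMI class. In the same example, P(BMI ≥ 29.5) = 1 − Φ(0.50) = 0.3085, and 0.0666/0.3085 = 0.22. About a fifth of the patients who would belong to a class of 30 and above would be missing from it.

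**Step 5: the age overlap.** Nobody is lost. For scale only: the protocol gives no age distribution for this trial, but section 1.2.6 reports a median age of 62 in MONALEESA-2. With a normal distribution centred there and an assumed SD of 10, Φ(0.9) − Φ(0.8) = 0.8159 − 0.7881 = 0.0278; with SD 13 the share is 2.5%. That is about 12-14 of 500 patients whose class is undetermined. This trial also admits premenopausal women, so its age distribution may differ.

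**The case against.** The strongest counter-argument is that this is a typing slip. The other two ordered lists in the section, age and therapy line, both end in >=, so >30 may simply stand for >=30. Likewise, with >= 70 explicit, 60-70 is most naturally read as 60 to under 70. The section is written in the past tense, so the models may already have been run with sensible classes, and SAP section 2.1 refers to a further analysis document (RAP 7.1) that is not available here. On that view nobody was dropped.

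Part of this stands: exclusion depends on literal coding, which the documents neither confirm nor rule out. It does not remove the defect. Because >= prints correctly elsewhere in the same list, the missing equals sign is probably not an extraction fault. The text as it stands is what a programmer or reader would follow, and if it is a slip the correction is the same.

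It is also fair to say that little depends on these models. The trial is described as exploratory, and no planned endpoint uses these classes. Leaving patients out on the value of a covariate mainly costs precision; no bias in an odds ratio has been shown.

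A reader might go further and infer that the neutropenia and ALT/AST events of these patients are lost to the safety assessment. The documents do not support that: under SAP section 2.8.1 the adverse event tables use all patients in the Safety Set as denominator.

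**Conclusion.** Both boundary errors are certain from the text: a rounded BMI of 30 has no class, and age 70 has two. If the classes are coded as written and the software drops records with an undefined class, patients with BMI 29.5 to under 30.5 leave both models. The size, about 3-10% or roughly 14-48 of 500, rests on the assumed BMI distributions and on the planned sample size, since the number of patients in the models is not given.

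Two stronger readings should be avoided. A single figure such as 6% lies inside the range but needs a chosen mean and SD that the documents do not supply. And the loss should not be attributed to both errors: only the BMI gap can remove patients, while the age overlap makes the assignment ambiguous.

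This is a minor point. It affects two exploratory models outside the protocol and leaves the safety tables and the primary and secondary endpoints untouched.

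**What to change.** In SAP section 2.13, state BMI as <20, 20-25, 26-29 and >=30 (after rounding), and age as <60, 60-69 and >=70. Every patient with a recorded BMI and age then has exactly one class, and the loss from class definitions is zero.

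Check the program against these classes and report the number of patients used in each model. If any patient was dropped, or if 70-year-olds were coded differently, rerun the two models.

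The cost is two small text edits, a program check and at most a rerun of two regressions; no new data are needed. Entering age and BMI as continuous covariates would also avoid the problem, but that is a different model and a matter of preference, not part of this correction.

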As of 5 Mar 2015, 668 patients were randomized; 334 patients each to the ribociclib plus letrozole arm and the placebo plus letrozole arm. The median study follow-up was 15.3 months, as of the 29-Jan-2016 data cut-off date, and the proportion of patients continuing to receive treatment in the ribociclib plus letrozole arm was higher than in placebo plus letrozole arm (58.4% vs 46.1%, respectively). Disease progression was the primary reason for treatment discontinuation and was more frequent in the placebo plus letrozole arm compared to the ribociclib plus letrozole arm (43.7% vs. 26%). Adverse events led to the discontinuation of study treatment in 32 patients (4.8%): 25 patients (7.5%) in ribociclib plus letrozole arm and seven patients (2.1%) in placebo plus letrozole arm.

The median age of patients was 62 years (range: 23-91) and 44.2% were of ≥ 65 years old. The majority of the patients were Caucasian (82.2%). All patients had ECOG performance status of either 0 or 1. Approximately one-third (34.0%) of the patients in this study were de novo breast cancer patients. Nearly two-thirds (58.8%) of patients had visceral disease (19.8% with liver and 45.4% with lung involvement) and 22.0% had bone only metastases at study entry. All except four patients had stage IV disease at the time of study entry (other four had stage III disease). One-third (34.0%) of the patients had ≥ 3 metastatic sites.

The median duration of exposure to study treatment was 13.0 months in the ribociclib arm and 12.4 months in the placebo arm. The median duration of exposure to ribociclib/ placebo was 12.2 months in the ribociclib arm and 12.4 months in the placebo arm; 240 patients (71.9%) were exposed to ribociclib plus letrozole therapy for ≥ 9 months. Median relative dose intensity was 87.5% for ribociclib and 100% for placebo. Ribociclib dose interruptions occurred in 257 (76.9%) patients, and letrozole was interrupted in 132 (39.5%) patients in the ribociclib arm. Placebo was interrupted in 134 (40.6%) patients and letrozole was interrupted in 107 (32.4%) patients in the placebo arm. Dose reductions occurred in 53.9% and 7.0% of patients in the ribociclib and placebo arms, respectively, most commonly for adverse events (169 [50.6%] vs. 14 [4.2%] patients; ribociclib vs. placebo arm). Dose reduction due to neutropenia occurred in 65% of patients who had a dose reduction due to AEs in the ribociclib arm.

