7. Patient has a histologically and/or cytologically confirmed diagnosis of estrogen-receptor positive and/or progesterone receptor positive breast cancer by local laboratory.
8. Patient has HER2-negative breast cancer defined as a negative in situ hybridization test or an IHC status of 0, 1+ or 2+. If IHC is 2+, a negative in situ hybridization (FISH, CISH, or SISH) test is required by local laboratory testing.
9. Patient must have either:
 - Measurable disease, i.e., at least one measurable lesion as per RECIST 1.1 criteria
OR
 - Bone lesions: lytic or mixed (lytic + sclerotic) in the absence of measurable disease
OR
 - Non-measurable disease (including osteoblastic bone lesions)

Note: Tumor lesions previously irradiated curatively or subjected to other locoregional therapy will only be considered measurable if disease progression at the treated site after completion of therapy is clearly documented.
10. Patient has an Eastern Cooperative Oncology Group (ECOG) performance status 0 or 1 or 2
11. Patient has adequate bone marrow and organ function as defined by the following laboratory values (as assessed by local laboratory):
 - Absolute neutrophil count $\geq 1.5 \times 10^9/L$
 - Platelets $\geq 100 \times 10^9/L$
 - Hemoglobin $\geq 9.0 \text{ g/dL}$
 - INR ≤ 1.5
 - Serum creatinine $< 1.5 \text{ mg/dL}$ or creatinine clearance $\geq 50 \text{ mL/min}$.
 - Total bilirubin $\leq \text{ULN}$ except for patients with Gilbert's syndrome (Morbus Meulengracht) who may only be included if the total bilirubin is $\leq 3.0 \times \text{ULN}$ or direct bilirubin $\leq 1.5 \times \text{ULN}$.
 - Aspartate transaminase (AST) $< 2.5 \times \text{ULN}$, except for patients with liver metastasis, who are only included if the AST is $< 5 \times \text{ULN}$
 - Alanine transaminase (ALT) $< 2.5 \times \text{ULN}$, except for patients with liver metastasis, who are only included if the ALT is $< 5 \times \text{ULN}$
12. Patient must have the following laboratory values within normal limits or corrected to within normal limits with supplements before the first dose of study medication:
 - Sodium
 - Potassium
 - Magnesium
 - Total Calcium (corrected for serum albumin in patients with hypoalbuminemia)
13. Standard 12-lead ECG values assessed by the local laboratory
 - QTcF interval at screening $< 450 \text{ msec}$ (using Fridericia's correction)

14. Resting heart rate 50-90 bpm

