Increase from baseline grade 0 or 1 to grade 2 (> 3.0 – 5.0 x ULN)	
Dose interruption of ribociclib
 
If resolved to ≤ baseline grade in ≤ 21 days, then maintain dose level
 
If resolved to ≤ baseline grade in > 21 days or toxicity recurs, then reduce 1 dose level
 
Repeat liver enzyme and bilirubin tests twice weekly for 2 weeks after dose resumption
 
If toxicity recurs after two dose reductions or recovery to ≤ baseline grade is > 28 days, discontinue ribociclib

Increase from baseline grade 0 or 1 to grade 3 (> 5.0 – 20.0 x ULN)	
Dose interruption of ribociclib until resolved to ≤ baseline grade, then lower 1 dose level of ribociclib
 
Repeat liver enzyme and bilirubin tests twice weekly for 2 weeks after dose resumption
 
If recovery to ≤ baseline grade is > 28 days, discontinue ribociclib
 
If toxicity recurs, discontinue ribociclib

Increase from baseline grade 2 to grade 3 (> 5.0 – 20.0 x ULN)	
Dose interruption of ribociclib until resolved to ≤ baseline grade, then lower 1 dose level of ribociclib
 
Repeat liver enzyme and bilirubin tests twice weekly for 2 weeks after dose resumption

	If toxicity recurs after two dose reductions or recovery to \leq baseline grade is > 28 days, discontinue ribociclib.
Grade 4 ($> 20.0 \times$ ULN)	Discontinue ribociclib
AST or ALT and concurrent Bilirubin	
For patients with normal ALT and AST and total bilirubin at baseline: AST or ALT $> 3.0 \times$ ULN combined with total bilirubin $> 2 \times$ ULN without evidence of cholestasis Or For patient with elevated AST or ALT or total bilirubin at baseline: baseline: [AST or ALT $> 2 \times$ baseline AND $> 3.0 \times$ ULN] OR [AST or ALT $8.0 \times$ ULN]- whichever is lower- combined with [total bilirubin $> 2 \times$ baseline AND $> 2.0 \times$ ULN]	Discontinue ribociclib
Confounding factors and/or alternative causes for increased transaminases should be excluded before dose interruption/reduction. They include but are not limited to: concomitant medications, herbal preparations or dietary supplements, infection, hepato-biliary disorder or obstruction, new or progressive liver metastasis, and alcohol intake.	

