7.1.1.2 Patient demographics and other baseline characteristics

The following assessments and procedures will be performed within 21 days prior the start of study treatment:

- Obtain patient's written informed consent form.
- General demography including age and gender.
- Medical history/current medical conditions (including prior concomitant medications within the last 4 weeks prior to Day 1).
- History and current disease status (including staging, diagnosis information, previous anti-cancer treatments and sites of disease). The following information must be collected for all previous anticancer therapies: date start, date end, setting (neoadjuvant, adjuvant, metastatic), best response, reason for treatment discontinuation.

Additionally, to determine eligibility at the screening visit, the following assessments will be performed:

- Physical examination, height and weight.
- Vital signs including blood pressure and heart rate.
- Existing ECG assessment can be used if it was within 7 days before first intake of study medication.
- ECOG performance status

- Safety laboratory assessments such as hematology, biochemistry, serum lipid profile, coagulation and urinalysis should be performed locally at the investigator's discretion and are not captured on the CRF. Laboratory assessments performed within 21 days prior to C1D1 may be used. If, at screening, laboratory results are out of range and clinically significant, these results should be captured on the medical history/current medical conditions CRF.
- Radiological tumor assessments at baseline:
 - CT for chest abdomen and pelvis unless performed within 28 days prior to C1D1. CT scan with contrast media should be used except for patients who are allergic/sensitive to the radiographic contrast media. CT for chest and abdomen may be replaced by MRI if clinically contraindicated, e.g. allergy/sensitivity to the radiographic contrast media, metastatic presentation, after prior consultation and approval by Novartis.
 - Brain: CT or MRI if CNS metastases are present unless performed within 28 days prior to C1D1.
 - Whole Body Bone Scan unless performed within 56 days prior to C1D1.

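### The exploratory ALT/AST model in SAP 2.13 includes bone metastases but leaves out baseline liver metastases, so it cannot identify them as a prognostic factor and its other odds ratios may be confounded

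*SAP*

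**What the plan says.** SAP 2.13 describes a "Multivariate regression analysis to identify prognostic factors for Neutropenia respectively AST/ALT increase". Of its status the SAP says: "This analysis was not foreseen in the study protocol but included on request of the principal investigator". Two models are fitted, one per event, and both use one covariate list: age (3 categories), BMI (4 categories), "Presence (no vs. yes) of bone metastases at study start", prior chemotherapy (yes/no) and therapy line (3 levels). On method: "The following effects (without interactions) were investigated by Type 3 estimates and Wald's confidence intervals for Odds ratios". The ALT/AST event is any adverse event coded to either preferred term. Bone is the only disease site in the list.

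The protocol connects liver metastases with transaminases in three places:
- Section 5.2, criterion 11: ALT must be below 2.5 x ULN, "except for patients with liver metastasis, who are only included if the ALT is" below 5 x ULN. AST has the same rule.
- Table 6-4 lists, among the confounding factors or alternative causes of raised transaminases, "infection, hepato-biliary disorder or obstruction, new or progressive liver metastasis, and alcohol intake".
- Section 6.2.1.2 includes liver metastasis in the work-up of possible drug-induced liver injury.

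Protocol 7.1.1.2 collects "previous anti-cancer treatments and sites of disease" at baseline, so the information should be in the database.

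**The concern.** A model meant to identify prognostic factors cannot identify one that is not offered to it. For a liver-enzyme outcome, liver metastases are an obvious candidate and the protocol itself points to them. Using one list for both events carried bone into the ALT/AST model without asking which disease site matters for that outcome.

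There is a second, conditional worry. If liver metastases raise the risk of an ALT/AST event and are unevenly spread over therapy line, prior chemotherapy or bone metastases, the fitted factors pick up part of their effect. A later therapy line could then be presented as a risk factor when part of the signal is liver disease. SAP 2.13 says these results are meant for presentation, and SAP 2.8.1.1 makes hepatobiliary toxicity an event of special interest, so readers may take the odds ratios seriously.

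**Working it through.** The plan gives no event count, effect size or precision for this model, so there is no figure of its own to reproduce.

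**Inputs**
- Documented proxies from the earlier first-line phase III trial (MONALEESA-2), Protocol 1.2.6: "19.8% with liver and 45.4% with lung involvement) and 22.0% had bone only metastases at study entry".
- Protocol Table 1-5: treatment-related ALT increase in 42 of 334 patients (12.6%), AST increase in 36 of 334.
- Planned N = 500.
- Assumed: event risk without liver metastases p0 = 12%; liver odds ratio (OR) 2 to 4; liver prevalence 30 to 40% in later lines; bone metastases in 60 to 70% of patients.

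**Formula.** Risk with liver metastases: p1 = OR·o/(1 + OR·o), where o = 0.12/0.88 = 0.1364. This gives p1 = 0.214, 0.290 and 0.353 for OR 2, 3 and 4. In a group with liver prevalence v, the risk is r = p0 + v(p1 − p0). The apparent odds ratio of a factor with no effect of its own is the ratio of r/(1 − r) between its levels. If v is equal in both levels, it is exactly 1.00 whatever the liver OR.

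**Therapy line** (true OR 1.0; v = 19.8% in first line)

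| Liver OR | later lines 30% | later lines 40% |
|---|---|---|
| 2 | 1.08 | 1.16 |
| 3 | 1.14 | 1.28 |
| 4 | 1.18 | 1.36 |

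For example, with OR 4 and 40%: r = 0.12 + 0.198 × 0.233 = 0.166 against 0.12 + 0.40 × 0.233 = 0.213, so the ratio of odds is 0.271/0.199 = 1.36.

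**Bone metastases** (true OR 1.0). The result depends on how often liver and bone disease occur together, which no document gives.
- Scenario 1: liver prevalence is 0.198/0.78 = 25.4% in everyone who is not bone-only, and 0 in bone-only patients. Among patients with bone metastases it is then 0.38 × 0.254/0.60 = 16.1% or 0.48 × 0.254/0.70 = 17.4%, against 25.4% without bone. Apparent OR: 0.86 to 0.94.
- Scenario 2: 80% of patients with liver metastases also have bone metastases. Prevalence is then 0.158/0.60 = 26.4% with bone against 0.040/0.40 = 9.9% without, or 22.6% against 13.2% if bone prevalence is 70%. Apparent OR: 1.08 to 1.33.

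The sign reverses between two scenarios that the documents cannot tell apart.

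**Parameters and events.** The model has 2 + 3 + 1 + 1 + 2 = 9 parameters besides the intercept; a liver term makes 10. At 12.6% of 500 there are about 63 events, so events per parameter fall from 7.0 to 6.3. If the ALT and AST counts did not overlap, 78/334 × 500 is about 117 events, and the figures are 13.0 and 11.7. The proxy counts treatment-related events in a first-line trial, while the SAP counts any ALT or AST event, so the true number may differ.

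**The case against.** The strongest reply is that confounding is not shown, and that stands. No section relates liver metastases to therapy line, prior chemotherapy or bone metastases in this trial. The protocol passages also do not prove a baseline effect: a raised ALT allowed at entry is not an adverse event unless it worsens after consent (Protocol 8.1.1), and Table 6-4 speaks of new or progressive liver metastasis, not presence at study start. Exclusion criterion 1 removes patients with symptomatic visceral disease. The passages make liver metastases a clear candidate; they do not supply an odds ratio.

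Imprecision is also a fair point. With a rough unadjusted calculation at 14 to 20% event risk, a bone odds ratio of 1.0 has a 95% interval of about 0.6 to 1.6 or 1.7. A later-line level of 75 patients (assumed) against the other 425 gives about 0.5 to 1.8 or 2.0. All the shifts above lie inside these intervals.

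The analysis is exploratory, has no hypothesis, and seeks prognostic rather than causal factors, so therapy line can be a valid marker even if liver disease explains it. This lowers the severity. It does not answer the main point: a prognostic search that leaves out an available candidate cannot report on it.

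It may also be said that baseline ALT and AST are equally obvious omissions. They are, but Protocol 7.1.1.2 does not routinely capture screening laboratory values on the CRF, whereas disease sites are collected.

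**Conclusion.** The gap in specification is real and rests on no assumption: the ALT/AST model cannot identify liver metastases as a prognostic factor. Confounding of the other odds ratios is possible, with size and direction unknown from the documents. Under the stated assumptions a null therapy-line odds ratio would appear as about 1.08 to 1.36, and a null bone odds ratio as anything from 0.86 to 1.33. No size can be given for prior chemotherapy, which may include neoadjuvant and adjuvant treatment and is not simply a marker of later-line disease.

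A reader might infer that all three effects are confounded, or that bone metastases will look protective. The documents support neither: with balanced liver prevalence there is no bias, and the bone result changes sign with an undocumented co-occurrence. A reader who assumed 15% liver prevalence in first line would get 1.12 to 1.48 for therapy line, but the only first-line figure in the documents is 19.8%.

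Severity is low. The clinical benefit rate, the secondary endpoints and the planned safety tables are untouched.

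**What to change.** In SAP 2.13, add to the ALT/AST model a yes/no term for liver metastases at study start, defined in the same way as the bone term. Leave the neutropenia model unchanged. State in the text and tables that the odds ratios are exploratory and descriptive, and report the number of events beside the number of parameters.

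The cost is one line of SAP text, one further parameter (10 instead of 9, with the small loss in events per parameter shown above) and, because the SAP reports these analyses in the past tense, probably a rerun. No new data collection is needed.
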